## 1. Introduction and Purpose

Historically, mechanical methods were the first methods developed to ripen the cervix or to induce labor (1). Dilapan-S®, a hygroscopic cervical dilator made of a patented hydrogel (AQUACRYL), works by absorbing fluid from the cells of the cervical canal, resulting in reversible cell wall dehydration and softening. The increase in volume of the rod(s) in turn, leads by mechanical stretch, to endogenous PG release with resultant cervical ripening. Dilapan-S® is approved by the FDA for cervical ripening in the third trimester. Recently a non-inferiority randomized trial at our center comparing Dilapan-S® to the most commonly used, but not FDA approved, mechanical dilator method (Foley balloon) was completed and results show that it is not inferior to the latter (<https://clinicaltrials.gov/ct2/show/NCT02899689>). The usual practice with mechanical ripening methods is to insert the mechanical dilator in the hospital and then await cervical ripening, which can take up to 12 hours. We believe that allowing the subject to go back home after insertion is a promising strategy that lowers in-hospital healthcare costs and improves subject satisfaction. Therefore, we propose a randomized controlled trial to compare the efficacy and safety of outpatient versus inpatient pre-induction cervical ripening with Dilapan-S® in pregnant women greater than 37 weeks.

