## 3. Concise Summary of Project

The **target population** for our study is women who present for induction of labor. If there is a decision by the obstetrical team to place a mechanical dilator for cervical ripening, the obstetrical team will notify the research staff so that the patient may be screened for the study. If the subject is eligible for the trial, written informed consent will be obtained by person-to-person contact. The PI, study coordinator, or a collaborator will be responsible for the informed consent procedure. After informed consent is obtained and Dilapan-S® is placed, the patient will be randomized to the Outpatient or the Inpatient group. Those randomized to the outpatient group will be asked to come back within 12 hours or sooner if contractions or other conditions arise.

Our **primary objective** will be to compare the hospital length of stay in the inpatient setting to the outpatient setting.

**Secondary objectives** will be to compare other clinical outcomes such as composite maternal and neonatal outcomes, vaginal delivery rate within 24 and 36 hours after admission, time to reach active stage of labor defined as  $\geq 6$  cm, change in Bishop score, rates of spontaneous and operative vaginal delivery, rate of cesarean delivery, adverse events, healthcare cost impact and subject satisfaction.

**Healthcare cost impact** will be assessed based on direct hospital costs or Medicaid charges, using cost minimization technique. In cost-minimization analysis, two or more interventions that have been assumed or shown to have the same effectiveness are compared for cost and the least expensive one is recommended from an economic perspective. The primary analysis will be performed for all those randomized including the costs/charges after randomization. A secondary analysis will be performed accounting separately for costs/charges before randomization.

**Secondary Analysis/ Metanalysis** will be performed for all those randomized as individual participant data meta-analysis all data from respective randomized controlled trials in the different centers, including from UTMB, will be de-identified. All centers will be requested to send the raw data for secondary analysis in an individual participant data meta-analysis. Research groups who share data will get the opportunity of a co-authorship in relation to the size of their study.

Data will be shared in a file that is encrypted and deidentified and password protected.

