Data to be collected will consist of maternal age and ethnicity, gravida/para, gestational age, height, weight, estimated fetal weight, reason for induction, date and time of device placement, date and time of delivery, mode of delivery, Bishop score at eligibility assessment, Bishop score prior to dilator insertion, Bishop score after removal or expulsion of dilator, date and time of rupture of membranes, date and time of device expulsion/removal, hospital length of stay, other intrapartum and obstetrical interventions, complications in device placement and cervical ripening, during labor and delivery including but not limited to meconium, infections, hemorrhage, fetal decelerations and subject satisfaction. We will also collect the amount of analgesics subjects received during device placement, cervical ripening and induction time (includes acetaminophen or intravenous medications or regional anesthesia). Data will be abstracted from the medical records as well as from direct interview. We will also collect basic neonatal data including birth weight, Apgar scores, rate of admission to neonatal intensive care unit, infections, and other neonatal complications. The data collected will not be used for clinical diagnosis or treatment purposes. Additional economic data to be collected includes the following admission direct costs or charges from the following services/departments: Blood Bank Transfusion Operations, Chemistry Division, Hematopathology Division, JSH Labor & Delivery unit, Materials Management, Microbiology Division, Mother Baby Unit, Pharmacy, Respiratory Care Services, Surgical Operating Suite.

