### **5.4. Pre-Induction**

#### **5.4.1. Group Assigned to Outpatient Cervical Ripening**

After Dilapan-S® placement, subject will be monitored for at least 30 minutes. If no contraindications, such as tachysystole, active vaginal bleeding, rupture of membranes or nonreassuring fetal testing (defined as minimal or absent variability, abnormal baseline, or presence of decelerations) evidence of labor, or other serious medical conditions deemed by the clinical staff or the attending physician to preclude outpatient cervical ripening develop after insertion, the subjects will be randomized. After randomization subject will record the pain she experienced during insertion in the patient's survey (see Appendix 3). Those subjects randomized to outpatient ripening will be given the option to either stay in a hotel or, if they are able to reach the hospital within 60 minutes, return home. The cost for the hotel will be covered by the study budget. Subjects at CUMC will solely be given the option to stay at home. Subjects will be allowed to ambulate, shower and perform regular activity during that period. "Nothing per vagina" will be allowed (incl. intercourse, tampons etc.). Subjects will also be instructed to return to L&D unit 12 hours after insertion, or earlier if any excessive bleeding, rupture of membranes, pain or other concerns (contractions, decreased fetal movement) develop before the 12 hours. Special leaflet (Appendix 2) will be provided to subjects leaving the hospital, with detailed instruction, emergency contacts to appropriate study/clinical staff and space to document of oral medication taken for pain relief (acetaminophen). Subject will also document the date and time of membrane rupture if applicable.

Reasons for examining or removing dilators earlier include but are not limited to:

- 1) Spontaneous onset of labor  
(defined as regular, firm, uterine contractions with an effaced cervix >80% and a cervical dilatation > 3 cm)
- 2) Other than category I fetal heart rate tracing  
(category I includes all: Baseline rate: 110–160 beats per minute, baseline FHR variability: moderate, absent late or variable decelerations, Early decelerations: present or absent and accelerations: present or absent)
- 3) Spontaneous rupture of membranes or need for amniotomy
- 4) Spontaneous expulsion of Dilapan-S® rods
- 5) Subject removed the rods herself

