### **6.2. Secondary Outcomes**

- Rate of vaginal deliveries (%)
- Rate of vaginal deliveries within 24 hours since admission to hospital (%)
- Rate of vaginal deliveries within 36 hours since admission to hospital (%)
- Time from hospital admission to reach active stage of labor defined as  $\geq 6$  cm (mins)
- Time from device placement to reach active stage of labor defined as  $\geq 6$  cm (mins)

- Change in Bishop score from insertion to extraction of device
- Change in cervical dilation after Dilapan-S®
- Rate of spontaneous vaginal deliveries after one round of cervical ripening (%) (no additional medical or mechanical interventions)
- Rate of operative vaginal deliveries (%)
- Rate of caesarean deliveries (%)
- Rate of artificial rupture of membranes (AROM) (%)
- Rate of epidural analgesia (%)
- Total duration of Dilapan-S® application (insertion to removal/extraction) (mins)
- Device placement to delivery interval (mins)
- Induction (Oxytocin/Prostaglandin initiation) to delivery interval (mins)
- Analgesia used during device placement (%), cervical ripening (%) and labor induction (%)
- Rate of adverse neonatal outcomes (composite and individual) –Apgar score <7 at 1-5-10 minutes, Cord arterial pH <7.1, neonatal ICU admission (%)
- Occurrence of maternal and neonatal complications within 2 weeks after delivery (%)
- Total duration of maternal hospital stay (hours)
- Subject reported clinical outcomes (sleep, rest, pain, activities of daily living, etc.) (Appendix 3)
- Subject reported satisfaction with Dilapan-S® treatment (Appendix 3)
- Medicaid charges for each hospitalized subject in both arms

*(Blood Bank Transfusion Operations, Chemistry Division, Hematopathology Division, JSH Labor & Delivery unit, Materials Management, Microbiology Division, Mother Baby Unit, Pharmacy, Respiratory Care Services, Surgical Operating Suite)*

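### The secondary cost outcome has two measures and two populations, names no NICU or readmission item, and may be tested without estimating the mean difference

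*Combined protocol and SAP*

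**What the plan says.** - **Section 3, healthcare cost paragraph.** Cost impact "will be assessed based on direct hospital costs or Medicaid charges, using cost minimization technique". On population and time window: "The primary analysis will be performed for all those randomized including the costs/charges after randomization". Costs incurred before randomization get a separate secondary analysis. The paragraph defines the technique as one in which "interventions that have been assumed or shown to have the same effectiveness are compared for cost".
- **Section 3, data-collection paragraph.** "Additional economic data to be collected includes the following admission direct costs or charges from the following services/departments", followed by ten departments. The same paragraph collects, for the newborn, "rate of admission to neonatal intensive care unit, infections, and other neonatal complications".
- **Section 6.2.** The secondary outcome is "Medicaid charges for each hospitalized subject in both arms", with the same ten departments and no time window.
- **Section 8.** Medicaid charge reports and direct cost reports are both named as sources, with no order between them.
- **Sections 5.6 and 5.7.** Hospital readmission is recorded to two weeks after delivery, from charts or, failing that, by phone.
- **Section 5.4.1.** If an outpatient does not come back, outside records are sought for the primary outcome. Cost is not mentioned.
- **Section 13.3.** Continuous variables are summarized (mean, SD and quartiles among others) and compared by t-test or Wilcoxon-Mann-Whitney test. No confidence interval is named, and there is no cost-specific method.

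**The concern.** Lower cost is part of the trial's rationale: section 1 holds that sending women home "is a promising strategy that lowers in-hospital healthcare costs and improves subject satisfaction". Readers will therefore use the cost result, and three features leave it less well defined than it should be.

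First, direct costs and charges are different quantities, and the plan does not say which one leads. Being hospitalized at a study site is also determined after randomization, so restricting to hospitalized women is not the same as analysing everyone randomized. Non-return from home can arise mainly in the outpatient arm.

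Second, the itemized total may leave out newborn intensive care and readmission, which the trial records as clinical events.

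Third, a cost comparison needs the difference in mean cost, because the mean multiplied by the number of women gives the total bill. A Wilcoxon test does not estimate that difference.

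At stake is whether the reported saving depends on choices made after the data are seen. The primary endpoint is not involved.

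**Working it through.** The plan gives no formula, variance, price or sample size for cost, so the main check is a comparison of the text.

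**1. Measure, population and window**

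| Section | Measure | Population | Window |
|---|---|---|---|
| 3 (cost paragraph) | direct costs or charges | all randomized | after randomization; earlier costs separate |
| 3 (data list) | direct costs or charges | not stated | the admission |
| 6.2 | Medicaid charges only | hospitalized women | not stated |
| 8 | both sources | not stated | not stated |

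The populations differ for randomized women with no study-hospital admission. The plan foresees them: section 5.8.2 gives failure to return from outpatient ripening as an example of loss to follow-up, and section 13.1 keeps such women in the All Randomized population.

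**2. Cost items.** The lists in sections 3 and 6.2 each contain 10 departments, and they are the same 10. NICU items: 0 of 10. Readmission items: 0 of 10. The Mother Baby Unit and Respiratory Care Services lines could hold some newborn cost.

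**3. How many NICU admissions might be involved.** Inputs: 188 per arm (section 13.4) and 6 NICU admissions among 444 registry women (section 3 table).

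- The 188 reproduces: 54% against 37.8%, 85% power and two-sided 0.05 give 169 per group (pooled variance, no continuity correction); 169/0.9 = 187.8, rounded up to 188; 2 × 188 = 376.
- Registry rate: 6/444 = 1.35%, exact 95% CI 0.50% to 2.92%.
- Expected per arm: 188 × 6/444 = 2.5 (0.9 to 5.5 across that interval).
- Expected in total: 376 × 6/444 = 5.1 (1.9 to 11.0).
- Three of the six cases were growth restriction (2) or a cardiac anomaly (1), which section 7.2 excludes if they are recognized before enrolment. Without them: 188 × 3/444 = 1.3 per arm.

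This assumes that the registry rate carries over. It counts events and does not price them.

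**4. Estimand.** Section 13.3 summarizes means, so a point difference can be obtained by subtraction. If the Wilcoxon option is chosen, the accompanying test concerns ranks, and nothing in the plan gives the precision of the mean difference.

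**The case against.** The strongest reply is that this is a secondary outcome whose scope is nearly stated. Sections 1 and 3 speak of in-hospital and admission costs, both data sources are planned, and section 13 defers detail to an SAP before database lock. The section 6.2 wording may simply presume that everyone is hospitalized. The verb in the section 3 list could be read as open-ended. A t-test remains available, and the absence of an interval is common to all secondary outcomes.

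Much of this stands, and it keeps the point small. It does not remove the mismatch between sections 3 and 6.2, and the open reading of the list is weakened because section 6.2 repeats the same ten items under the outcome itself.

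Three stronger readings are tempting, and the documents do not support them:

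- **That omitting the hotel biases the result.** The hotel is an outpatient-only resource, not offered at CUMC, and "The cost for the hotel will be covered by the study budget". It is neither a hospital cost nor a Medicaid charge, so leaving it out follows from the implied perspective.
- **That the choice of population could shift the outpatient mean by 10%.** With k women costed at zero, the mean falls by k/188; k = 188 − 169 = 19 gives 10.1%. That needs a zero-cost rule that no section states, and the arm's whole drop-out allowance as women without bills. Missing bills are more naturally missing data, as section 5.7 treats unobtainable outcomes.
- **That non-significant clinical tests will be taken as equal effectiveness.** Such tests could not show it: 9 against 3 NICU admissions per 188 gives p = 0.08 by uncorrected chi-square. But section 3 allows equal effectiveness to be assumed, and no section treats non-significance as equivalence.

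**Conclusion.** The concern holds in a narrow form. Sections 3 and 6.2 contradict each other on measure and population, and section 8 does not settle the measure. The itemized list names no NICU or readmission cost, so the total may be incomplete; the direction is unknown, and part of the newborn cost may already be counted. The Wilcoxon option would leave the mean cost difference without an interval.

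The effect on the reported saving cannot be computed, because the documents give no prices, no expected number of non-returners and no rule for their costs. On the registry rate, only about 1 to 3 NICU admissions per arm are expected, so any effect would come from a few, possibly costly, cases. This is a desirable correction to a secondary outcome. The primary endpoint and the sample size of 376 stand.

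**What to change.** In sections 3 and 6.2, or in the SAP that section 13 promises:

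1. Name one lead measure, direct costs or charges, and report the other as supportive. Align section 8.
2. Analyse all randomized women by assigned arm, with the section 3 time window. Treat unavailable bills as missing rather than zero and report their number by arm. A mean over available bills is still a mean over women with bills, so that count shows how far the two populations diverge.
3. Report the mean cost difference with a 95% confidence interval, for example by bootstrap, whichever test is used.
4. Add NICU and known two-week readmission costs as a sensitivity analysis, first establishing what the Mother Baby Unit line already contains so that nothing is counted twice.
5. State the hospital or payer perspective. Under it the hotel stays outside the main total and may be reported separately.

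Keep the planned separate analysis of costs before randomization.

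The price is a few extra billing abstractions. Readmissions elsewhere that are known only by phone may remain uncosted, so their number should be given. The saving may look smaller or less precise, which is a reason to keep the added items in a sensitivity analysis.

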## 5. Study Procedures

### VISIT #1

#### 5.1. Screening, eligibility assessment, consenting and baseline data collection

After institutional review board (IRB) approval, pregnant women who have a plan of care for induction of labor at term will be approached by the principal investigator or any of the co-investigators for participation in the study. Informed consent for this study can be obtained during several different phases of interaction with the patient:

Phase 1: At any antenatal obstetrical office visit when decision is made to schedule subject for induction of labor.

Phase 2: Potential subjects presenting for induction of labor at term in the “Labor and delivery” unit (L&D).

Subjects willing to participate in the study will be evaluated for their eligibility including their Bishop score. The latter will be obtained from the medical record after the initial pelvic exam which is standard of care in our unit. Subjects will be reassured that participation in the study is voluntary and will not interfere with diagnosis or treatment of her condition. The subjects will receive the same care and expertise as any other subject treated in our unit. Subjects are approached in a private patient room, and written consent will be obtained by direct person-to-person contact. The principal investigator, study coordinator, or a collaborator will be responsible for the informed consent. Non-English-speaking subjects are anticipated to be part of the study population and informed consent will be provided in their primary language. We will also be using the teach back method; briefly the potential subject will be asked to explain in their own words what they need to know or do, we will also ensure they understand the study and, whenever needed, re-explain to them about the study procedures and risk of participating in the trial. After obtaining informed consent, and Dilapan-S® is successfully placed (see section 4.2) and after 30 minutes period of observation, subjects who remain eligible will be randomized to management as inpatient versus outpatient (see section 4.3).

#### 5.2. Placement of synthetic osmotic cervical dilator

Placement of the Dilapan-S® will be performed by trained medical personnel. After informed consent is obtained, Dilapan-S® will be placed as follows:

Before the device placement, subjects will undergo continuous cardiotocography (CTG) monitoring for 30 minutes while fetal condition and uterine activity are monitored. The cervix is visualized with a sterile vaginal speculum and cleaned with iodine or chlorohexidine. As many synthetic osmotic cervical dilators (Dilapan-S®, Medicem Technology s.r.o., Kamenne Zehrovice, Czech Republic) as possible are inserted into the cervical canal under direct visualization. Synthetic osmotic dilators are inserted into the cervical canal with special attention to cross through the internal os.

The number of Dilapan-S® rods inserted will vary, depending on the status of the cervix for the particular subject. Synthetic osmotic dilators will be inserted as per manufacturer’s instructions (IFU –

Appendix 1). After insertion, the subject will be evaluated for excessive bleeding, pain or other concerns by the clinical providers (see section 4.4). The synthetic osmotic dilators will be left in place for at least 12 hours, and no longer than 24 hours. Subjects will be instructed, that under no circumstances they should try to remove Dilapan-S® themselves. If subject removes the device herself, such act will constitute protocol deviation and the subject will be assessed for cervical ripening within Intent-to-Treat analysis (see section 4.4 for details) but will not be included in the Per-Protocol-Population analysis.

In the rare event that the Dilapan-S® cannot be inserted or contraindications for outpatient management develop during insertion or during the observation period after the insertion but before randomization (subject changed her mind and desires to stay inpatient, significant vaginal bleeding during insertion, non-reassuring fetal heart rate, rupture of membrane, intractable pain or other concerns the providers or investigators feel that patient cannot be managed as an outpatient), then the subject will not be randomized nor included in the analyses. These subjects will be considered as screening failures and managed as inpatient according to standard practice and under the direction of the clinical team. Refer to section 4.8.1 for further details.

### **5.3. Randomization**

After Dilapan-S® placement, and if the subject remains eligible, subject will be randomized to the outpatient group or the inpatient group. A confidential computer-generated simple randomization scheme will be prepared and provided by independent vendor (PharmTest, s.r.o., Czech Republic) to our study coordinator. The currently used randomization code will be replaced by 2 randomization codes, 1 of them for CUMC site (both clinics will use the same randomization sequence. The randomization envelopes to be used at CUMC will be provided by UTMB).

A randomization log with group assignment, subject name, and medical record *number* will be used to track the randomization process. The subject will be included in the analysis by intent-to-treat once the randomization assignment has been made.

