**Randomization** will be performed using a computer-generated random list of numbers assigning subjects to the 2 groups of the study. This list of random number assignments will be kept secure in an opaque envelope until the end of the study. 2 randomization sequences will be required for UTMB and CUMC sites.

No significant adverse effects are expected with the use of Dilapan-S® for mechanical dilation as an outpatient when compared to inpatient setting. The most common adverse events from cervical ripening with mechanical dilators such as the Foley balloon have been reported to be less than 1% (8), the most common being pain (0.26%), unintended amniotomy (0.04%), vaginal bleeding (0.07%), non-reassuring fetal heart tracing (0.07%), and uterine tachysystole (too low to quantify). Our group also reported the following adverse effects with inpatient use of Dilapan-S® for cervical ripening in a group of 444 subjects (9):

Maternal and neonatal adverse events	Nr. of cases (%)	Comments (n)
Uterine tachysystole	1 (0.2)	
Non reassuring fetal heart rate	1 (0.2)	
Maternal complications/discomfort	15 (3.4)	Bleeding during insertion/extraction of dilators (12), Cramping/pain (1), Other (1)
Uterine contractions	111 (25)	Tocography during cervical ripening showed low frequency and mild intensity contractions
Maternal infection	14 (3.2)	Chorioamnionitis (9), Urinary tract infection (3), Endomyometritis (1), Wound infection (1)

NICU admission	6 (1.4)	Meconium aspiration (2), Growth restriction (2), Asphyxia (1), Congenital cardiac abnormality (1)
Neonatal infection	1 (0.2)	Neonatal sepsis (maternal group B Streptococcus was not observed prior IOL)

The most significant potential risks noted with Dilapan-S® occur during or shortly after insertion and include vaginal bleeding due to cervical trauma and incidental rupture of membranes, as well as pain or discomfort with placement. If these occur and are persistent (i.e. unresolved pain despite analgesia), subjects will be admitted for delivery (as they require maternal monitoring) and will not be randomized, since they do not fulfill the eligibility criteria to receive the outpatient intervention.

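### Allocation concealment is not assured as written: the scheme goes to a role that may take consent, and randomisation can be withheld on judgement after insertion

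*Combined protocol and SAP*

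**What the plan says.** **Who receives the scheme.** Section 5.3: "A confidential computer-generated simple randomization scheme will be prepared" and "provided by independent vendor (PharmTest, s.r.o., Czech Republic) to our study coordinator".

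**Who may take consent.** Section 3: "The PI, study coordinator, or a collaborator will be responsible for the informed consent procedure". Section 5.1 repeats this.

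**What happens between insertion and randomisation.** Randomisation follows consent, insertion and at least 30 minutes of observation (sections 5.1 and 5.4.1). Section 5.2 lists reasons not to randomise. Some are observable events, such as ruptured membranes or significant bleeding. One is the woman's own wish to stay in hospital. The last is open-ended: "or other concerns the providers or investigators feel that patient cannot be managed as an outpatient". Women withheld in this way are not randomised and are left out of the analyses.

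**How the list is kept.** Section 3: "This list of random number assignments will be kept secure in an opaque envelope until the end of the study". The same section calls for two sequences, one for UTMB and one for CUMC. Section 5.3 adds, about the CUMC code, that "both clinics will use the same randomization sequence" and that UTMB will provide the envelopes used at CUMC.

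The text available for review does not say whether per-subject envelopes are sealed, opaque or sequentially numbered, who opens them, or whether final eligibility is recorded first. The randomisation log in section 5.3 holds assignment, name and record number.

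**The concern.** Concealment requires that nobody who decides whether a woman enters the trial can know her assignment beforehand. Here the role that receives the scheme may also enrol, and an unstructured judgement on entry is made just before assignment. The protocol does not describe a barrier between the two.

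The setting of care cannot be masked, and staff may have a view on which women suit outpatient ripening. If the next assignment were known, women expected to stay long could be withheld when it was outpatient and randomised when it was inpatient. That would lower the rate of stays over 48 hours in the outpatient arm with no treatment effect. Intention-to-treat analysis does not correct it, because the selection comes before randomisation.

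It would also be hard to detect. Section 5.2 calls women withheld after insertion screening failures, but section 5.8.1 defines a screening failure only as a consented woman in whom the device was not placed. Section 13.1 (Safety Population) picks up inserted but non-randomised women only if they had complications attributed to the device.

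**Working it through.** **1. The plan's own figure.** Inputs from section 13.4: control rate 0.54, outpatient rate 0.378, two-sided alpha 0.05, power 85%. With pooled variance under the null and mean rate 0.459:

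n = [1.960·√(2·0.459·0.541) + 1.036·√(0.54·0.46 + 0.378·0.622)]² / 0.162² = (1.381 + 0.721)² / 0.02624 ≈ 168.3, rounded up to 169.

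169/0.90 = 187.8, so 188 per group and 376 in total. The stated size reproduces, and this point does not change it. The planned effect is 16.2 percentage points.

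**2. The passages side by side.**
- Section 5.3 puts the scheme with the coordinator, and sections 3 and 5.1 allow that role to take consent. No sentence found separates the two tasks.
- Section 3 closes the list until study end, while section 5.3 has assignments made from the scheme and envelopes supplied to CUMC. One closed list cannot also be the working source. The statements fit together only if section 3 means a master copy, which it does not say.
- Section 5.2 gives the power to withhold to providers or investigators. Section 5.4.1 speaks of clinical staff or the attending physician. Neither asks for the decision to be recorded before assignment.

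**3. When the discretion biases the comparison.** If the next assignment is unknown, withholding affects both arms alike. It narrows the population but does not bias the difference. Under simple randomisation, past assignments do not predict the next one. Bias therefore needs access to the list or to the contents of an envelope.

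**4. Size if it happened.** Assumptions, none of them from the documents: no true effect (0.54 in both arms), and a share *e* of women bound for the outpatient arm, with long-stay risk *r*, withheld only from that arm. The outpatient rate becomes

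p = (0.54 − e·r)/(1 − e).

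Type I error is approximated by Φ(d/SE − 1.96) + Φ(−d/SE − 1.96). Here d = 0.54 − p and SE is the pooled standard error with 188 inpatient and 188(1 − e) outpatient women (about 0.052 to 0.053).

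| r | e | p | d (points) | two-sided type I error |
|---|---|---|---|---|
| 0.74 | 5% | 0.503/0.95 = 0.5295 | 1.1 | 5.5% |
| 0.74 | 10% | 0.466/0.90 = 0.5178 | 2.2 | 7.0% |
| 0.90 | 5% | 0.495/0.95 = 0.5211 | 1.9 | 6.5% |
| 0.90 | 10% | 0.450/0.90 = 0.5000 | 4.0 | 11.7% |

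Exact binomial calculation with 188 against 179 or 169 women gives 5.5%, 7.1%, 6.6% and 11.8%. At *r* = 0.90, nearly all the excess is false benefit for outpatient care, which rises from 2.7% with no selection to 5.5% and 11.5%. These shares mean withholding 0.05·188 ≈ 9 to 0.10·188 ≈ 19 outpatient-bound women.

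**The case against.** The plan does contain safeguards. An independent vendor prepares the scheme and it is called confidential. The list is kept in an opaque envelope, envelopes are used at CUMC, and UTMB and CUMC have separate sequences. Simple randomisation prevents guessing from earlier assignments. Excluding unsuitable women before randomisation is the right order, and section 5.2 introduces these cases as rare and ties the judgement to whether the woman can be managed as an outpatient. All of this stands. A reader might infer that allocation is unprotected, and the documents do not support that.

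Three further inferences also go too far.

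- *That the coordinator is the person who enrols.* The coordinator is one of three roles that may take consent. Consent can be taken at an antenatal visit, and the decision to withhold is not assigned to the coordinator. Bias needs the extra step that the decision-makers learn the next assignment.
- *That the shared sequence reveals assignments.* It would do so only if each clinic held a copy of the same ordered list. Two clinics drawing from one numbered set reveal nothing to each other, and the text does not say which is meant.
- *That a false-positive rate near 12% is to be expected.* It rests on a 90% risk with no source in the documents. At 74% risk the range is about 5.5-7%.

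The objection does not remove the gap. The safeguards describe where the list comes from and how it is stored. They do not stop its recipient, who may enrol, from knowing the next assignment. The one concrete measure, the envelope closed until study end, cannot apply as worded to a list in use.

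**Conclusion.** The point holds as a weakness in concealment as specified: the protocol does not keep knowledge of the next assignment away from those who consent women or judge their eligibility. Nothing in the documents shows that assignments were or would be disclosed, and without disclosure the discretion causes no bias between arms.

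If disclosure and selective withholding did occur at the assumed 5-10%, the spurious difference would be about 1 to 4 points against a planned 16.2. Two-sided type I error would be about 5.5-7% at a long-stay risk of 74% and about 6.5-12% at 90%. That is modest, but it cannot be corrected in the analysis and is cheap to prevent. The change should be made, though the gap does not by itself invalidate the design.

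**What to change.** 1. In section 5.3, have the vendor keep the master list and supply sequentially numbered, sealed, opaque per-subject envelopes, or assign centrally. State that no one who consents women or judges eligibility sees the list.
2. Require the final post-insertion eligibility decision to be recorded with signature and time before the envelope is opened.
3. Log every woman withheld after insertion with the reason, and align the screening-failure definition in section 5.8.1 with section 5.2.
4. State how the two CUMC clinics draw assignments: from one common numbered envelope set, or from a sequence each. They should never hold copies of the same ordered list.
5. Limit the sentence in section 3 about the opaque envelope to the vendor's master list.

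The cost is minor protocol wording, envelope preparation by the vendor, one added log field and at most one extra sequence. With sealed envelopes opened only after the eligibility record, the existing coordinator can still handle them, so no separate allocator is needed. Sample size and clinical rules are unchanged.
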